3. CHARACTERISTICS OF RESEARCH POPULATION

3.1. NUMBER OF SUBJECTS

This is a single site study at the University of Rochester Medical Center, with an accrual goal of 30 fully evaluable subjects. "Fully evaluable" as defined as completing informed consent, meeting eligibility criteria, initiating Silverlon® dressing during radiation therapy and continuing to two weeks after completion of radiation therapy. Therefore, the 30 fully evaluable subjects must complete full protocol procedures. Assuming a 20% withdrawal rate, we will recruit 36 eligible subjects. Subjects who initiated treatment but withdraw from the study will be used in the intent to treat analyses. In the past year, the Wilmot Cancer Institute had 75 patients that would be eligible for this study which demonstrates our ability to reach our accrual goal. To reach this goal of 30 fully evaluable subjects, the total number of subjects approached and/or consented may reach 75 subjects.

PARTICIPANT POPULATION(S)

Accrual Number:	Category/Group: (Adults/Children Special/Vulnerable Populations)	Consented: Maximum Number to be Consented or Reviewed/Collected/ Screened	Intent to Treat: Number to enroll and initiate treatment.	Fully Evaluable: Number to enroll and fully complete study.
Local	75/0/0	75	36	30
Study-wide	75/0/0	75	36	30
Total:	75/0/0	75	36	30

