6.1 USE OF TOPICAL AGENTS FOR WORSENING SKIN REACTIONS

In an effort to prevent moist desquamation and reduce patient withdrawal from study, use of standard of care topical medications may be allowed only under the following circumstances:

• Subject should have documented worsening skin reaction that requires additional treatment per the treating physician, and be ordered/prescribed the topical agent by the

Page 27 of 41 RSRB STUDY00004587 Version Date: 09/14/2021 NCT04238728

- treating provider on study.
- The type, dose and frequency of the medication prescribed will be documented in the subject's study and medical record.
- The subject will be instructed to remove the Silverlon® dressing before applying the topical agent, and reapply the dressing approximately one (1) hour after application of the topical agent to allow for absorption into the skin. The subject will be asked to document the removal and re-application of the dressing in their Subject Compliance Log.

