7. SUBJECT WITHDRAWALS

Subjects will be advised during the consent process that they have the right to withdraw from the study at any time without prejudice or reason. Subjects that withdraw from the study will be replaced with another subject. Subjects will continue to receive radiation therapy as prescribed with standard of care with their treating radiation oncologist. The reason for discontinuation will be recorded in the subject's medical records. The date of occurrence and reasons for any subject withdrawal will be recorded and documented on the **Withdrawal Form**.

Subjects can be withdrawn from the study by the investigator or radiation oncologist for: non-compliance to study procedures; termination of funding; allergic reaction to Silverlon® dressing; worsening of the disease under study; intercurrent illness; pregnancy; or progression of skin reaction to RTOG score ≥3 in the radiation area where the Silverlon® dressing has been applied (i.e., whole breast). RTOG score ≥3 requires patients to have areas moist desquamation outside of skin fold regions (i.e., which would exclude inframammary fold and axillas because these are skin fold regions). Additionally, an area of moist desquamation that is >50% of the radiation treatment area (i.e., RISRAS-HPA score ≥3). Therefore, a large area of moist desquamation outside of skin folds would suggest withdrawal. Pinpoint areas and fold areas of moist desquamation could not require withdrawal. Patients withdrawn from the study will stop using Silverlon® dressing, but continue to receive radiation therapy on their normal schedule as prescribed by the treating radiation oncologist. For patients withdrawn from the study, standard of care for radiation dermatitis will be provided by the treating radiation oncologist, who will continue to follow the patient as per their normal clinical routine. The date of occurrence and reasons for any subject withdrawal will be recorded and documented on the Withdrawal Form. An adverse event will be reported if the skin reaction is RTOG ≥4. This grade of radiation dermatitis is severe and should be reported on the AE Source Doc and following reporting procedures stated in §10. Allergic reaction to Silverlon® dressing will be reported as an unexpected side effect on the AE Source Doc.

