8. EARLY STOPPING PROCEDURES

The study will be stopped if we observe a significantly increased rate of confluent moist desquamation (i.e., RTOG \geq 3; large areas (>50% of radiation treatment area) of moist desquamation outside of skin folds) in subjects using the Silverlon® dressing. The study will be stopped if 6/15 or fewer subjects who initiated treatment with Silverlon® dressing are withdrawn due to RTOG score \geq 3. This result would suggest a two-fold increase in the rate of confluent moist desquamation with patients using Silverlon® dressing. If the first 6 subjects are withdrawn due to RTOG score \geq 3 while using the dressing (i.e., 6/6), the study will be stopped due to the significantly increased rate of confluent moist desquamation. If the study is stopped early, participant reimbursement will be issued to any subjects remaining on study.

Page 28 of 41 RSRB STUDY00004587 Version Date: 09/14/2021 NCT04238728

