9.2. PROTECTION AGAINST RISKS

The study protocol, amendments to the protocol, consent forms, study forms and patient-report forms are reviewed by the responsible IRB, University Research Subjects Review Board (RSRB), prior to implementation. The RSRB also provides continuing review of study conduct and consent.

The research staff (*PI, Co-investigators, study coordinator*) will conduct continuous review of data and subject safety. The review will include the number of subjects, adverse reactions, and responses observed. The Investigator will submit summaries of this data to the Research Subjects Review Board (RSRB) for review as required in the study's protocol review committee approval letter.

Study forms and patient-report forms are either electronic forms through REDCap, excel spreadsheets, or paper forms. All data from paper forms will be entered electronically into REDCap database as it is received from the subjects. All electronically captured data will be securely stored in the secure REDCap database at the University of Rochester Medical Center. To protect the confidentiality of subjects, questionnaires and data collected on each subject will be coded, the form collected will contain a numerical Subject ID and Subject Initials. The forms contain the minimum personal identifiers needed for research. The key list with all Subject IDs will be kept in a locked file. All forms will also be kept in a locked file that is separate from the key list that links the subject name and the code number. When data analyses are completed, the key list and paper forms will be destroyed. The required informed consent will be the only record kept of those subjects who have participated in the research. The Silverlon® dressing that will be studied in this project is not associated with any risks.

Any safety information for an individual patient that is volunteered by a study participant during the course of this research will be documented. All adverse events, whether observed by the Investigator, radiation oncologist, or nurse, elicited from or volunteered by the subject, will be documented and reported as described in §10. Each adverse event will include a brief description of the experience, the date of onset, the date of resolution, the duration and type of experience, the severity, contributing factors, and any actions taken. This description will be in the summary not during a subject's regularly scheduled clinic appointment.

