11. DATA AND SAFETY MONITORING PLAN

[name] (co-investigator) in Radiation Oncology at University of Rochester will serve as the Clinical Monitor for this study. Approval of protocol, informed consent

Page 32 of 41 RSRB STUDY00004587 Version Date: 09/14/2021 NCT04238728 procedures, and recruitment will be obtained from the University RSRB. Any safety concerns about the clinical protocol will be brought to the immediate attention of the Principal Investigator and Co-investigator. Study personnel will follow aforementioned reporting procedures for adverse event reporting, including any serious adverse events. Protocol deviations and quality issues will be recorded and reported to the IRB per local policies. Remedial and/or corrective action to prevent reoccurrence of protocol deviations or quality issues will be instituted as necessary. Because this study's procedures pose relatively low risk to subjects, monthly data and procedural reviews by the Clinical Monitor and Investigator in consultation with study personnel will be sufficient to identify and ameliorate any potential safety issues. As such, an additional Data and Safety Monitoring Plan document will be not be created for this study.

Patients will have their radiated sites examined once a week by either a radiation oncologist as part of their regular course of radiation therapy. At this examination, any adverse events related to their skin will be recorded. For the purpose of this study, an adverse event will be defined as severe radiation dermatitis meeting the definition of RTOG score grade 4 or above (ulceration, hemorrhage or necrosis) or other adverse reaction of Grade 3 or higher in the area of radiation area where Silverlon® dressing is applied. Patients meeting the definition of 'adverse event' will be withdrawn from the study and the radiation dermatitis then treated according to local protocol as ordered by the attending radiation oncologist. Changes in dose or scheduling of radiation therapy in response to an adverse event will remain the responsibility of the attending radiation oncologist.

If a patient feels that they are having an adverse event outside of the weekly monitoring schedule, they may contact the study coordinator or principal investigator by phone and an immediate follow-up appointment with the radiation oncologist will be arranged.

12. STUDY MONITORING PLAN – Sponsor

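### On its intended reading, section 8 states no stopping count for initiators 16 to 36 (21 of 36, 58%); they rest on an unquantified commitment to stop

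*Combined protocol and SAP*

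**What the plan says.** Section 8 (Early Stopping Procedures) opens with a commitment that has no end point: "The study will be stopped if we observe a significantly increased rate of confluent moist desquamation". It then gives two counts. The main one is "The study will be stopped if 6/15 or fewer subjects who initiated treatment with Silverlon® dressing are withdrawn due to RTOG score" ≥3. The other stops the study if the first six subjects are all withdrawn for that reason. The section interprets the main count as follows: "This result would suggest a two-fold increase in the rate of confluent moist desquamation with patients using Silverlon® dressing". It does not give the reference rate that is doubled.

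The table in section 3.1 puts 36 under "Intent to Treat: Number to enroll and initiate treatment", and section 13.1 uses the same number. Section 7 says that withdrawn subjects are replaced, so initiators could exceed 36.

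Other provisions apply throughout:
- Section 6.1 covers worsening skin: "use of standard of care topical medications may be allowed only under the following circumstances".
- Section 7 lets the investigator or radiation oncologist withdraw a subject at RTOG ≥3: "Therefore, a large area of moist desquamation outside of skin folds would suggest withdrawal".
- Under section 11, a subject with RTOG grade 4 or above, or another reaction of Grade 3 or higher under the dressing, "will be withdrawn from the study and the radiation dermatitis then treated according to local protocol".
- Section 9.2 says the research staff "will conduct continuous review of data and subject safety" and that summaries go to the review board. Section 10.3 sends summaries to a Data Safety Monitoring Committee. Section 11 adds monthly reviews by the Clinical Monitor and the Investigator.

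None of these states a number of events at which the study as a whole stops.

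**The concern.** The literal wording of the main limit is garbled, because it would stop the study for six or fewer withdrawals. The sensible repair is six withdrawals among 15 or fewer initiators, with 6/6 as a special case. On that reading the counts end at the 15th initiator, although more than half of the planned initiators come later.

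This leaves an inconsistency inside the section. It treats 6/15 as the sign of a doubled rate, but five events in the first 15 and two more in the next two subjects give 7/17, a higher proportion, with no stated count reached. After subject 15 the commitment to stop still binds, but those applying it must decide without a number what a significantly increased rate is. The study is unblinded, has no control group and has safety as its primary objective, so a limit fixed in advance would make a decision to continue easier to defend. The per-patient rules bound harm to each subject. They do not say when accrual should end.

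**Working it through.** **Inputs.** Limit of 6 among 15 or fewer (section 8); 36 initiators (sections 3.1 and 13.1); completion in 12 months (section 13.1); 15 to 40 fractions (section 3.5); dressing worn until 2 weeks after radiation (section 2.1). Assumed: every RTOG ≥3 event leads to withdrawal, events are independent, and 36 initiators in 12 months means 3 a month, so a monthly check falls at n = 18, 21, …, 36.

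**1. The plan's own number.** 30 × (1 + 0.20) = 36, as stated.

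**2. Share beyond the last count.** 36 − 15 = 21, and 21/36 = 58%.

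**3. The section's own proportion.** 6/15 = 40%. If 40% is a doubling, the reference rate is 0.40/2 = 20%. This is an inference; section 8 does not state it.

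**4. Courses that reach no stated count.** 5/15 followed by 2/2 is 7/17 = 41%. The extreme is 5/15 followed by 21/21, that is 26/36 = 72%.

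**5. Chance of passing subject 15.** With X ~ Binomial(15, 0.40), P(X ≤ 5) = 0.403.

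**6. Chance of stopping by subject 36.** Let S(n, k) be the probability of having k events after n subjects without a stop. Then S(n, k) = (1 − p)·S(n − 1, k) + p·S(n − 1, k − 1), and any mass at or above the limit for n is moved to stopped. The stated rule uses limit 6 for n ≤ 15 and none afterwards. The extensions add 40% of n, rounded up. The tighter limits are looks at 8/20, 9/25, 11/30 and 12/36, each with a binomial tail under 20% no larger than that of 6/15.

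| True rate | Stated counts only | 40% carried on, monthly | 40% carried on, every subject | Tighter limits |
|---|---|---|---|---|
| 20% | 6.1% | 6.8% | 7.5% | 9.9% |
| 25% | 14.8% | 17.4% | 19.3% | – |
| 30% | 27.8% | 34.2% | 37.2% | 49.5% |
| 40% | 59.7% | 73.7% | 76.7% | 87.9% |

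The first column gives the unquantified sentence no chance of stopping the study after subject 15. Differences from that column are therefore upper bounds on the gain.

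**7. Size of the saving at a true 40% rate, monthly checks.** Expected subjects fall from 21.61 to 20.16 (1.5) and events from 8.64 to 8.06 (0.6). These figures ignore subjects already on the dressing when a limit is crossed. At an assumed five fractions a week, 15 to 40 fractions take 3 to 8 weeks; adding 2 weeks gives 5 to 10 weeks, or about 4 to 7 subjects at 3 a month. With that overlap (400,000 simulated studies) the average saving is 0.93 subjects and 0.38 events at overlap 4, and 0.58 and 0.23 at overlap 7. In the 14% of studies that stop only because of the extension, the saving averages 4 to 7 subjects and 1.6 to 2.7 events.

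**8. How demanding a flat 40% becomes.** Binomial tail under 20%: 6.1% for 6/15, 3.2% for 8/20, 0.9% for 12/30 and 0.25% for 15/36. By contrast, 12/36 has a tail of 4.2%.

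**The case against.** The strongest case against is that the study is not left without a rule. The opening sentence of section 8 is mandatory and has no end point, and it is backed by continuous and monthly review with summaries to the review board and a committee. A reader might infer that the later 21 initiators are unprotected, or that the study would run on to 26/36. The documents do not support either inference. What stands is narrower: none of these safeguards carries a number.

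Section 8 also describes 6/15 as a rate, so a running 40% proportion is another possible repair of the garbled sentence. On that repair the gap disappears. Section 8 does not say so, however, and its only denominators are 15 and 6.

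A front-loaded limit is also a legitimate choice for a marketed dressing judged a non-significant risk. With 4 to 7 subjects on treatment at once, outcomes among the first 15 can still stop the study when about 19 to 22 have started. Both points stand and lower the weight of the finding. They do not explain why 40% matters at subject 15 and has no stated consequence at subject 17.

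Finally, a flat 40% asks for ever stronger evidence as numbers grow (step 8). Printed alone, a table of such counts could be taken to define a significantly increased rate and so weaken the open-ended promise. This stands, and it shapes the fix.

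**Conclusion.** The gap is real and small. On the intended reading, section 8 states no count for 21 of the 36 planned initiators (58%; more if replacements take the total above 36). A true rate of 40% passes the last stated count in 40% of studies. Carrying 40% forward at monthly checks would raise the chance of stopping from 60% to at most 74%, and the average saving is under one subject after overlap. The 14-point difference should not be read as the gain over the plan as written, because the baseline leaves out a rule that still binds.

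These figures rest on the assumed accrual of 3 a month, on independent events, and on every RTOG ≥3 event leading to withdrawal, which section 7 leaves to judgement. The 20% reference rate is inferred. Individual subjects are protected by the per-patient limits. Low severity: CONSIDER, as a cheap improvement.

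**What to change.** In section 8:
1. Reword the main limit as six or more withdrawals for RTOG ≥3 among 15 or fewer initiators, and state the reference rate behind the two-fold claim.
2. State that the 40% criterion continues as a minimum trigger for every subject who initiates the dressing, replacements included, checked at the monthly section 11 review. Example counts are 8 at n = 18–20, 10 at 23–25, 12 at 28–30 and 15 at 36 (40% of n, rounded up).
3. State that this trigger is in addition to the general commitment to stop for a significantly increased rate, and does not replace it.

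Once the reference rate is stated, the sponsor may prefer tighter later limits. If it is 20%, looks at 8/20, 9/25, 11/30 and 12/36 would stop 88% of studies at a true 40% rate and 9.9% at 20%.

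The drafting cost is two sentences or a short table in section 8 and a line in section 11, using reasons already recorded on the Withdrawal Form. The statistical cost of carrying 40% forward monthly is more stops at lower rates: about 0.6 points at 20%, 2.6 at 25% and 6.4 at 30%. An unneeded stop would lose the precision planned with 30 and 36 subjects.

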9. RISK/BENEFIT ASSESSMENT

9.1. POTENTIAL RISKS

The proposed study is a low risk safety clinical trial. The only patient intervention in this study is the application of Silverlon® dressings to the radiation site. No adverse reactions or events have been reported for Silverlon® dressings. Subjects may find the dressing uncomfortable to wear inside the bra. However, discomfort while wearing has not been reported. Unexpected side effects, such as allergic reactions, may occur and are unpredictable. This reaction may be mild, such as a skin rash, or you may have more severe symptoms like swelling of the throat, low blood pressure, and shortness of breath. If any of these unexpected side effects occur, subjects will be advised to stop use of their intervention immediately. Subjects will be informed about any additional potential risks if they are discovered. Furthermore, while we make every effort to keep all data and study information private, this cannot be guaranteed. All data will be de-identified and stored in a locked file in a locked office. All appropriate procedures will be taken to maintain subject privacy and data collected during this study.

9.2. PROTECTION AGAINST RISKS

The study protocol, amendments to the protocol, consent forms, study forms and patient-report forms are reviewed by the responsible IRB, University Research Subjects Review Board (RSRB), prior to implementation. The RSRB also provides continuing review of study conduct and consent.

The research staff (*PI, Co-investigators, study coordinator*) will conduct continuous review of data and subject safety. The review will include the number of subjects, adverse reactions, and responses observed. The Investigator will submit summaries of this data to the Research Subjects Review Board (RSRB) for review as required in the study's protocol review committee approval letter.

Study forms and patient-report forms are either electronic forms through REDCap, excel spreadsheets, or paper forms. All data from paper forms will be entered electronically into REDCap database as it is received from the subjects. All electronically captured data will be securely stored in the secure REDCap database at the University of Rochester Medical Center. To protect the confidentiality of subjects, questionnaires and data collected on each subject will be coded, the form collected will contain a numerical Subject ID and Subject Initials. The forms contain the minimum personal identifiers needed for research. The key list with all Subject IDs will be kept in a locked file. All forms will also be kept in a locked file that is separate from the key list that links the subject name and the code number. When data analyses are completed, the key list and paper forms will be destroyed. The required informed consent will be the only record kept of those subjects who have participated in the research. The Silverlon® dressing that will be studied in this project is not associated with any risks.

Any safety information for an individual patient that is volunteered by a study participant during the course of this research will be documented. All adverse events, whether observed by the Investigator, radiation oncologist, or nurse, elicited from or volunteered by the subject, will be documented and reported as described in §10. Each adverse event will include a brief description of the experience, the date of onset, the date of resolution, the duration and type of experience, the severity, contributing factors, and any actions taken. This description will be in the summary not during a subject's regularly scheduled clinic appointment.

Page 29 of 41 RSRB STUDY00004587 Version Date: 09/14/2021 NCT04238728

9.3. POTENTIAL BENEFITS TO THE SUBJECTS

It is not possible to predict whether subjects will feel any personal benefit from participation in this research study. Subjects may have relief of radiation dermatitis and associated pain and itching, as well as improved quality of life. The study will provide insight into the safety and use of Silverlon® dressing for radiation dermatitis. Subjects will receive reimbursement for their participation in this study (See §5.6).

